6.2 Definition of analysis subgroups

Not applicable

7 Statistical methods

Statistical analyses will be performed by the CRGA.

7.1 General information on statistical analysis methods

7.1.1 Software

Statistical analyses will be performed with SAS software version 9.4 or later. Some graphs can be made with R software version 2.11 or later.

7.1.2 Adjustments to SSP

Adjustments may be made to this analysis plan in case of amendments to the protocol, or if phenomena not initially foreseen require statistical adaptations. In all cases, these modifications must be made before the database is frozen.

7.1.3 Agreements concerning dates and durations

Time since inclusion will be defined as the time since the day of inclusion, with the day of inclusion considered as day 1.

The time since the start of treatment will be defined as the time since the day of the first treatment, the day of the first treatment being considered as day 1.

Therefore, the durations will be calculated according to the following rule, for example for the duration between death and inclusion: day of death - day of inclusion **+ 1**.

The day before the day of inclusion (*resp.* the day before the day of treatment) will be considered as day -1 (day 0 does not exist).

The last date of news will be by default the date of the last examination/monitoring performed.

The following conversion rules will be used to convert the number of days into months or years: 1 month = 30.4375 days; 1 year = 365.25 days.

7.1.4 Outlier Conventions

Outliers will be subject to a confirmation request to the investigating center. In case of confirmation, their value will not be modified and will be taken into account as it is during the analysis.

7.1.5 Missing Data Conventions

Except in the cases specified, missing data will not be replaced.

In case of partially missing data concerning dates, the following rule will be applied: when the day is missing, the day will be considered as the 15th of the month.

7.1.6 Definition of the baseline

Baseline measurements will be the last measurements taken at inclusion. In case of missing data, the last measurement performed before the first administration of the treatment will be used.

7.1.7 Statistics

Quantitative variables will be described using the number, median, mean, standard deviation of the mean, minimum, maximum, and interquartile range (Q1-Q3). Quantitative variables may be categorized using their median or a cut-off known from the medical literature.

Categorical variables will be described using percentages, and if necessary their two-sided 95% confidence intervals (calculated using the exact method).

Missing values will not be included in the calculation of frequencies and percentages.

The **confidence intervals** provided will be two-sided 95% confidence intervals, except for the primary criterion where a one-sided 95% confidence interval will be given.

Survival data will be estimated and plotted using the Kaplan-Meier method (Kaplan and Meier, 1958).

This will be described by the median and rates calculated at different times. Two-sided 95% confidence intervals will be provided. Confidence intervals for the rates will be constructed from the Greenwood variance calculated using the log-log transformation.

The median follow-up time will be calculated using the reverse Kaplan-Meier method (Shemper, 1996).

For uni and multivariate analyses, hazard ratios will be estimated using a Cox model (Cox, 1984). The proportionality of the rates will be tested using the graphical representation and the test based on Schöenfeld residuals (Grambsch, 1994); the linearity of the effect of the continuous variables on the risk will be assessed from the graphical representation of the martingale residuals. Confidence intervals for the coefficient estimates of the Cox models will be calculated using the Wald method.

7.2 Patient characteristics at inclusion

7.2.1 Eligibility

Population ITT

Patient eligibility at inclusion will be verified and described by:

- Number and percentage of patients who met all inclusion criteria
- Number and percentage of patients who met all non-inclusion criteria
- Number and percentage of patients who met all criteria (inclusion and non-inclusion)

7.2.2 Demographic characteristics

Population ITT and CP

The following characteristics at inclusion will be described:

- Inclusion center (number of patients included per center)
- Age (year)
- Gender (Male vs Female)

7.2.3 Clinical characteristics

Population ITT and CP

The following characteristics at inclusion will be described:

- WHO general status (0 vs 1 vs 2)
- BMI (kg/m²)

- Presence of carcinoid heart disease (Yes vs. No)

7.2.4 Biological characteristics

Population ITT and CP

The following characteristics at inclusion will be described:

- Presence of anti-coagulant (Yes vs No)
- Chromogranin A (ng/mL)
- Urinary 5HIAA (mg/24h)
- Albumin (g/L)
- Total bilirubin (μmol/L)
- Conjugated bilirubin (μmol/L)
- PAL (Number of x the normal)
- ALT (Number of x normal)
- ASAT (Number of x normal)
- Hemoglobin (g/dL),
- PNN (/mm³)
- Wafers (x10³ /mm³)
- Creatinine clearance (ml/min)
- B Viral serology: HBsAg (Negative vs. Positive); and if Positive :
 - HBV-DNA (Negative vs Positive)
 - Anti-HBs Ac (Negative vs Positive)
 - Anti-HBc Ac (Negative vs Positive);
- Viral C serology: HCV antibody (Negative vs. Positive)

7.2.5 Characteristics related to the disease

Population ITT and CP

The following characteristics at inclusion will be described:

- The grade of the tumor (G1 vs G2)
- The site of the primary tumor (Esophagus vs Jejunum-Ileon vs Appendix vs Stomach vs Colon vs Rectum vs Other); A listing of other locations will be provided.
- The presence of bilateral liver metastases (Yes vs. No)
- Percentage of liver invasion;
- The presence of extrahepatic metastases (Yes vs. No), and if yes, the location;
- Presence of previous treatments:
 - Surgery of the primary (Yes vs. No),
 - Locoregional treatment of liver metastases (Yes vs. No) and if yes,
 - Type of treatment (Surgery and/or Radiofrequency and/or Other)
 - History of somatostatin analogue treatment (Yes vs. No) and if yes,
 - Treatment in progress (Yes vs. No)
 - The aim of the treatment (anti-tumor vs functional)
 - Other previous treatment (Yes vs. No)

7.3 Monitoring characteristics

Population ITT

The median follow-up time and its 95% confidence interval will be calculated in months.

7.4 Evaluation of the primary endpoint

Population CP

The rate of patients alive without progression at 24 months will be calculated and presented using its one-sided 95% confidence interval (exact confidence interval, binomial distribution).

The results for the primary endpoint will also be described by a Water Fall plot representing for each patient the percentage change at 24 months in liver metastasis size since the measurement at inclusion according to the response according to the RECIST V1.1 criteria.

7.5 Evaluation of effectiveness

7.5.1 Rate of living patients without liver progression in mRECIST at 24 months

Population CP

The 24-month live progression-free rate in mRECIST will be calculated and presented using its one-sided 95% confidence interval (exact confidence interval, binomial distribution).

7.5.2 Survival without liver progression

CP, ITT and PP population (if the number of patients allows it)

The time scale considered will be the month.

Progression-free survival will be plotted using the Kaplan Meier estimator. Median survival and rates at different time points will be calculated along with their 95% confidence intervals.

7.5.3 Progression-free survival

CP, ITT and PP population (if the number of patients allows it)

The time scale considered will be the month.

Progression-free survival (hepatic or not) will be plotted using the Kaplan Meier estimator. Median survival and survival rates at 4, 8, 12, 18, 24 months will be calculated along with their 95% confidence intervals.

7.5.4 Overall survival

CP, ITT and PP population (if the number of patients allows it)

The time scale considered will be the month.

Overall survival will be plotted using the Kaplan Meier estimator. Median survival and survival rates at 4, 8, 12, 18, 24 months will be calculated along with their 95% confidence intervals.

7.5.5 Best response

Population CP, ITT and PP

The best response under treatment (CR, PR, S, P) will be calculated and described according to the usual descriptive statistics. The objective response rate (OR = CR and PR) will also be described.

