5.7.2 Secondary endpoints of effectiveness

5.7.2.1 Rate of living patients without liver progression in mRECIST at 24 months

The rate of living patients without liver progression 24 months after inclusion will also be described according to mRECIST criteria and based on centralized review.

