5.7.1 Other criteria

- The evolution of the WHO performance index
- Best response under treatment (based on centralized review)
- The administration of G-CSF

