6.1 Definition of Analysis Populations

6.1.1 Intent-to-treat (ITT) population

The intention-to-treat population is defined as all patients included in the study, regardless of eligibility criteria and treatment received. All analyses will be performed on an intention-to-treat basis, unless specifically mentioned for certain criteria.

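### Best response in ITT has no not-evaluable category and missing values leave the percentages, so any included patient without a central reading raises the reported objective response rate

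*SAP*

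**What the plan says.** **Best response.** SAP 7.5.5 names the populations as "Population CP, ITT and PP" and lists complete response, partial response, stable disease and progression: "The best response under treatment (CR, PR, S, P) will be calculated and described according to the usual descriptive statistics". It adds: "The objective response rate (OR = CR and PR) will also be described". It gives no not-evaluable class and no denominator. SAP 5.7.1 (Other criteria) makes central review the source, without an investigator fallback.

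**Missing values.** SAP 7.1.5: "Except in the cases specified, missing data will not be replaced". No case is specified for best response. SAP 7.1.7: "Missing values will not be included in the calculation of frequencies and percentages".

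**ITT.** SAP 6.1.1 (Intent-to-treat population): "The intention-to-treat population is defined as all patients included in the study, regardless of eligibility criteria and treatment received".

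**mRECIST rate.** SAP 5.7.2.1 says that the 24-month rate "will also be described according to mRECIST criteria and based on centralized review", and SAP 7.5.1 assigns it to the CP population. The primary RECIST rate (SAP 5.7.1, Main criterion) also uses central review, but takes the investigator's opinion where review is impossible. Hepatic and overall progression-free survival (SAP 5.7.2.2 and 5.7.2.3) have the same fallback.

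**The concern.** A patient with no central reading fits none of the four categories. That makes the value missing, and 7.1.7 takes it out of the percentage. The table headed ITT would then describe only patients with a reading, in conflict with the SAP's definition of ITT. Patients lost in this way cannot be responders, so losing them can only push objective response upwards.

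The documents foresee such patients. Protocol VI.2 forbids everolimus when embolization is definitively cancelled after inclusion, and those patients stay in ITT. SAP 5.7.2.2 has a censoring rule for living patients with no morphological evaluation. The CP population is not immune: SAP 6.1.2 (primary endpoint population) treats a patient who dies after treatment as evaluable and as a failure for the primary endpoint, yet a patient who dies before any scan has no best-response category.

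At stake is a descriptive efficacy figure that readers would take at its ITT label, and the comparability of the RECIST and mRECIST 24-month rates.

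**Working it through.** **1. The plan's own figures.** SAP 5.5 and 5.6.1 give 35% under H0, 50% under H1, one-sided 5%, 80% power, 68 evaluable patients and success at 31 or more. The exact binomial reproduces them:
- P(X ≥ 31 | n = 68, p = 0.35) = 0.0461; a cut-off of 30 would give 0.0752.
- P(X ≥ 31 | n = 68, p = 0.50) = 0.8019.
- 68 / 0.95 = 71.6, rounded up to 72.

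None of these depends on best response or on the mRECIST rate.

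**2. Objective response in ITT.** Let x be the number of responders and m the number of included patients without a central reading.
- Over all included patients: x / 72.
- Under 7.1.7: x / (72 − m).
- Ratio of the two: 72 / (72 − m), which exceeds 1 whenever m ≥ 1, whatever x is (x > 0).

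The documents give neither x nor m. With x = 14 **assumed**:

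| m (assumed) | Rate under 7.1.7 | Rate over all included | Difference (points) |
|---|---|---|---|
| 4 | 14/68 = 20.6% | 14/72 = 19.4% | 1.1 |
| 7 | 14/65 = 21.5% | 19.4% | 2.1 |
| 11 | 14/61 = 23.0% | 19.4% | 3.5 |
| 14 | 14/58 = 24.1% | 19.4% | 4.7 |

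Differences are taken before rounding.

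**3. The 24-month mRECIST rate.** Take 68 CP patients, 31 successes over the full population, and 7 living patients without a usable central reading. The 7 is an assumption, about 10% of 68.
- Full CP denominator: 31/68 = 45.6%, exact one-sided 95% lower bound 35.2%.
- Worst case, all 7 unread patients being failures and dropped: 31/61 = 50.8%, lower bound 39.6%.
- If the 7 succeed at the same rate as the rest: 31 × 61/68 = 27.8, about 28 successes, and 28/61 = 45.9%. This equals 45.6% apart from rounding to whole patients.

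So the mRECIST rate need not be biased, but its denominator can still differ from that of the primary rate.

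**The case against.** **Best response under treatment is arguably not defined for a patient who was never treated.** Whether such a patient belongs in the denominator is a choice of estimand. That is fair, but SAP 7.5.5 names ITT and SAP 6.1.1 defines it regardless of treatment received. If another denominator is meant, the table needs another label. Early deaths and withdrawals after the start of treatment remain in any case.

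**The effect is conditional.** With a central reading for every included patient, nothing changes. This stands: the documents support a rule that overstates the rate when readings are missing, not a known overstatement.

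A reader might also infer four stronger points that the documents do not support:
- *That early deaths cannot lower the mRECIST rate.* SAP 5.7.2.1 counts patients who are alive without liver progression, so a death before 24 months is already a failure.
- *That the 5% allowance implies a planned inflation of 72/68.* SAP 5.5 excludes death from that allowance, and SAP 6.1.2 ties it to patients without a 24-month evaluation. With CT every 3 months (Protocol VIII.1), many of those could still have a best response. The row with 4 missing is only an assumed value.
- *That the mRECIST rate would read 50.8% instead of 45.6%.* That is the worst case in step 3.
- *That unread patients should all be mRECIST failures, or that an investigator fallback was forgotten.* The first could turn a RECIST success on the investigator's opinion into an mRECIST failure merely for want of a readable scan. As to the second, Protocol VIII.1 asks sites for RECIST 1.1 measurements only, so an investigator mRECIST reading may not exist.

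**Conclusion.** The point holds for best response. As written, SAP 7.5.5 and 7.1.7 together take included patients without a central reading out of a rate labelled ITT. Objective response is then too high by the factor 72/(72 − m). The size cannot be taken from the documents; under the assumed 14 responders and 4 to 14 missing readings it is 1.1 to 4.7 percentage points. The same can happen in CP for a treated patient who dies before any scan.

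For mRECIST only a narrower point holds: living patients without a usable central reading may be in the RECIST denominator and out of the mRECIST one. SAP 7.5.1 names CP but does not say how they are handled.

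The issue is minor. Best response is listed among other criteria, the mRECIST rate is descriptive, and neither carries a decision rule.

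**What to change.** - **SAP 7.5.5:** add a category for patients who are not evaluable or have no post-baseline assessment. Compute objective response over all patients in the named population (all included patients for ITT), counting this category as non-response. State this as an explicit exception to 7.1.7.
- **SAP 7.5.1:** report how many living CP patients lack a usable central mRECIST reading and say how they are handled. Show the RECIST and mRECIST 24-month rates side by side in patients who have both readings.

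The cost is a few sentences, one extra table row and one small comparison table. Stated response rates become slightly lower. SAP 7.1.2 requires changes before the database is frozen, so the denominator should be settled by then and not chosen once the data are known.

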7.6 Assessment of tolerance

7.6.1 Embolization or chemoembolization

Population ITT

Treatment by (chemo)embolization will be described by:

- The number of embolizations (1 vs 2) per patient and the total number of embolizations performed
- The number of chemoembolizations performed and the type: by doxorubicin or streptozotocin
- The number and percentage of patients who had (of the population of patients who had at least one embolization/chemoembolization):
 - 1 single embolization session
 - 1 single chemoembolization session
 - 2 embolization sessions
 - 2 sessions of chemoembolization
- Cross-tabulation of the number of embolizations or chemoembolizations planned in the PCR (at inclusion) and the number of embolizations or chemoembolizations actually performed.

Will also be described (percentage on the total number of embolisations and/or chemoembolisations performed):

- The territory of (chemo)embolisations
- The presence of a complication during the procedure (No vs. Yes), and if so:
 - presence of hepatic arterial occlusion by dissection or spasm (No vs. Yes)
 - presence of bleeding at the puncture site (No vs. Yes)
 - presence of another complication (No vs. Yes)
- The presence of a post-session complication (No vs. Yes), and if yes, a listing of these complications.

7.6.2 Administration of oral everolimus treatment

7.6.2.1 Duration of treatment

Population SP

The duration of treatment (converted into months) will be calculated by the formula :

$$\text{Start date of last intake} - \text{start date of first intake} + 1 \text{ day}$$

Temporary stoppages and any deferral days during this period will not be subtracted from this duration. It will be described according to the usual descriptive statistics.

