- For patients with bilobar involvement, each lobe must be treated separately. A catheter is placed in a lobar hepatic artery for total embolization. The second session should be performed on the other lobe.
- The use of a microcatheter is recommended in case of localized disease in order to obtain an ultra-selective positioning

Patients with localized lesion(s) should be treated with an even distribution of the dose of doxorubicin or streptozotocin within the lesion(s). If possible, chemoembolization should be repeated in the same manner. The two sessions should be separated by 4 to 8 weeks.

For patients with bilobar involvement, each lobe should be treated separately. A catheter is placed in a lobar hepatic artery and the full dose of doxorubicin/lipiodol or streptozotocin/lipiodol is administered. The second session should be performed in the other lobe.

Embolization or chemoembolization must always be associated with appropriate analgesic treatment, prophylactic antibiotic therapy and/or premedication with corticosteroids, the modalities of which are left to the discretion of the investigator.

Repeat chemoembolization sessions:

Three sessions are planned with intervals of 6 to 8 weeks.

The second and third session will be performed depending on the initial tumor response. An additional session is not recommended in case of complete lipiodolated fixation of all tumor targets.

In case of bleeding and/or severe liver failure secondary to an embolization or chemoembolization session, the following session(s) will be cancelled. For any other toxicity secondary to a TACE session, the performance of one (or two) additional sessions will be left to the discretion of the investigator.

Lipiodol and doxorubicin or streptozotocin are reported to health authorities as non-investigational drugs.

However, the tolerance of 2 embolization or chemembolization sessions will be collected in the observation booklet.

2- Everolimus treatment

Everolimus, an investigational treatment, is being provided as part of the study. It will be supplied in boxes of 30 tablets. The tablets will be either 10 mg or 5 mg. The boxes will be labeled "clinical trial" as recommended.

The dosage is 10 mg/day, i.e. 1 tablet of 10 mg or 2 tablets of 5 mg. In case of toxicity, refer to paragraph VII for dose adjustments.

Everolimus treatment will be continued for a maximum of 24 months after the first embolization or chemoembolization.

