Everolimus will be started 7 days after embolization or chemoembolization or when liver toxicities have returned to a grade ≤ 1 according to the NCI CTIC version 4.0 toxicity scale. Treatment should not be initiated beyond 30 days after embolization or chemoembolization.

If embolization or chemoembolization cannot be performed after patient inclusion, everolimus MUST NOT be started.

If embolization or chemoembolization is postponed, wait for embolization or chemoembolization to start everolimus as described above. If embolization or chemoembolization is definitely cancelled, DO NOT ADMINISTER everolimus and follow the patient according to the recommendations (see paragraph VIII-2: monitoring after cessation of treatment).

For the second session, everolimus will be stopped the day before the session and restarted in the same manner as initially, i.e., 7 days after embolization or chemoembolization or when liver toxicities have returned to a grade ≤ 1 according to the NCI CTIC toxicity scale version 4.0 and within a maximum of 30 days after embolization or chemoembolization.

Method of administration

Everolimus should be taken orally once a day at the same time each day, with or without food. The tablets should be swallowed whole with a glass of water. The tablets should not be chewed or crushed.

If a dose is missed, the patient should not take an additional dose, but should take the next prescribed dose.

3- Concomitant treatments to be avoided

Everolimus is a substrate of CYP3A4 and a moderate inhibitor of P-glycoprotein (PgP). Therefore, the absorption and subsequent elimination of everolimus may be influenced by drugs that act on CYP3A4 and/or PgP. In vitro, everolimus is a competitive inhibitor of CYP3A4 and a mixed inhibitor of CYP2D6.

Known and theoretical interactions with selective inhibitors and inducers of CYP3A4 and PgP are described in the Table below.

CYP3A4 and PgP inhibitors that may increase everolimus concentrations: CYP3A4 or PgP inhibitors may increase blood levels of everolimus by decreasing the metabolism or efflux of everolimus from intestinal cells.

CYP3A4 and PgP inducers that may decrease everolimus concentrations: Substances that are CYP3A4 and PgP inducers may decrease blood levels by increasing everolimus metabolism or efflux of everolimus from intestinal cells.

Effect of other active substances on everolimus

Active substances by interaction	Recommendations for Concomitant Administration
Potent CYP3/PgPA INHIBITORS	

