7.6.2.2 Doses administered

Population SP

Compliance will be calculated according to the formula: cumulative dose received (in mg) / protocol dose (in mg)

The theoretical protocol dose being equal to 10 mg x treatment duration (in days).

It will be described according to the usual descriptive statistics.

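### If everolimus dosing is recorded in multi-day periods, ending treatment duration at the start of the last intake shortens duration and inflates compliance

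*SAP*

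**What the plan says.** SAP 7.6.2.1 (Duration of treatment) computes duration as the "Start date of last intake" minus the "start date of first intake", plus one day. It adds: "Temporary stoppages and any deferral days during this period will not be subtracted from this duration".

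SAP 7.6.2.2 (Doses administered) defines compliance as cumulative milligrams received over protocol milligrams, and fixes the denominator: "The theoretical protocol dose being equal to 10 mg x treatment duration (in days"). The duration from 7.6.2.1 therefore feeds straight into compliance.

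On dosing, Protocol VI.2 says: "Everolimus should be taken orally once a day at the same time each day". It also sets the ceiling: "Everolimus treatment will be continued for a maximum of 24 months after the first embolization or chemoembolization". Protocol VII.2 requires interruptions and dose changes to be recorded, but does not describe the layout of the dosing record.

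Duration and compliance are listed among the tolerability criteria in SAP 5.7.3, and treatment duration and doses received appear in Protocol XII.2. Both are summarised descriptively in patients who took at least one dose of everolimus.

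**The concern.** A single tablet has a date; it does not have a start date. Applying a start date to both the first and the last intake fits a record that has a beginning and an end, such as a period at one dose level or the interval between two visits. The protocol's requirement to record interruptions and changes points the same way.

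Under that reading the formula stops the clock on the day the last period opens. The days in that period are lost from the duration. The tablets taken during it would normally still count in the cumulative dose, so the ratio has a full numerator over a shortened denominator.

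The loss is a fixed number of days, so it matters most when treatment is short. Patients who stop early are the ones in whom a tolerance analysis most needs accurate exposure. A value above 100% would be noticed. A reduced dose intensity that happens to read as nearly full compliance would not, and with a single arm there is no comparator to expose it.

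**Working it through.** The documents give no duration or compliance figure to reproduce, so the check is of the formulas themselves.

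**Inputs from the documents**
- Day count: last date minus first date plus 1 (SAP 7.6.2.1; same convention in SAP 7.1.3).
- Protocol dose: 10 mg per day (SAP 7.6.2.2).
- 1 month = 30.4375 days (SAP 7.1.3).

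**Assumptions, not in the documents**
- Length L of the last dosing record: one day, one month or three months. The 3-month value follows the visit interval in Protocol VIII.1. The monthly value follows the monthly visits mentioned in Protocol XII.2 and the boxes of 30 tablets in Protocol VI.2.
- True dose intensity of 85%.
- The cumulative dose includes the last record. The SAP does not say how it is built.

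**Formulas**, with T the true number of days from first to last dose:
- Duration as written: D = T − L + 1.
- Inflation factor for compliance: T / D.
- Compliance as written: 0.85 × T / D.

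**Results**

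| Record length | Treatment | T (days) | D (days) | T / D | Compliance as written (true 85%) |
|---|---|---|---|---|---|
| one daily dose | any | T | T | 1.00 | 85% |
| 1 month | 24 months | 730.5 | 701.1 | 1.04 | 89% |
| 1 month | 12 months | 365.25 | 335.8 | 1.09 | 92% |
| 1 month | 6 months | 182.6 | 153.2 | 1.19 | 101% |
| 3 months | 24 months | 730.5 | 640.2 | 1.14 | 97% |
| 3 months | 12 months | 365.25 | 274.9 | 1.33 | 113% |
| 3 months | 6 months | 182.6 | 92.3 | 1.98 | 168% |

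Example for the 12-month, 3-month-record row: D = 9 × 30.4375 + 1 = 274.9; 0.85 × 365.25 / 274.9 = 1.13.

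The duration itself is short by L − 1 days: 30.4 − 1 = 29.4 days with monthly records and 91.3 − 1 = 90.3 days with 3-month records.

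The 24-month rows run slightly past the ceiling, which is counted from the first embolization. With a start 7 days later, T = 730 − 7 = 723. A 91-day record then gives D = 633 and 0.85 × 723 / 633 = 97%, so the picture is the same.

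**A case that would go unnoticed.** Take T = 365, with 182 days at 10 mg and 183 days at 5 mg: 1,820 + 915 = 2,735 mg. True compliance is 2,735 / 3,650 = 74.9%. With a 91-day last record, D = 275 and the formula gives 2,735 / 2,750 = 99.5%.

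**A case that would be noticed.** A patient with a single 91-day record at full dose has D = 1 day and a ratio of 910 / 10 = 9,100%.

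**The case against.** The strongest reply is that the literal reading contains no error. Everolimus is a once-daily tablet, so the date of the last intake is the date of the last dose, and last minus first plus one is correct. The English is a rough translation, and two words in it are thin evidence of how dosing is captured. The case report form is not available. Record length, the 85% intensity and the make-up of the cumulative dose are all assumed. A one-day duration for a patient with one record is so plainly absurd that an analyst would correct it.

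Most of this stands. It rules out stating as fact that duration is understated and compliance overstated, a conclusion a reader might draw from the formula alone. It does not remove the ambiguity: the text as written supports two programs that give different answers, and the period reading is the likelier one for a quantity with a start date.

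A reader might also infer that the denominator wrongly penalises the pause around the second session, since "everolimus will be stopped the day before the session and restarted in the same manner as initially", and that those days should be subtracted. The documents do not support that. SAP 7.6.2.1 keeps stoppages in the duration by explicit choice, which makes the ratio a measure of dose intensity. Without liver toxicity the pause is about 8 days (1 before the session and 7 after). Anything longer, up to the 30-day limit after the session, is delay for toxicity, which a tolerance analysis should show. SAP 7.6.2 already reports temporary stops and the gap after the second session separately, under its headings on modified dosage and on other criteria.

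**Conclusion.** The point holds in conditional form and is minor. If dosing is recorded in multi-day periods and the cumulative dose includes the last one, duration is short by the length of that period less one day, and compliance is inflated by T / D. Over the scenarios shown, that factor runs from 1.04 (24 months, monthly records) to 1.98 (6 months, 3-month records). If an intake is one daily dose, there is no error. The factor depends on record length and time on treatment; the compliance percentages also depend on the assumed 85% intensity.

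The consequence is limited to descriptive results. Nothing in the primary endpoint, the sample size or the rule of 31 successes in 68 evaluable patients uses this duration. The per-protocol population does require one month of everolimus, but the SAP does not say that this is computed with the 7.6.2.1 formula. If it is, the same correction should carry over.

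**What to change.** In SAP 7.6.2.1, define duration as the date of the last everolimus dose actually taken (the end date of the last dosing record) minus the date of the first dose, plus one day. State in SAP 7.6.2.2 that the compliance denominator uses this same duration. Leave the rule on temporary stoppages as it is.

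This wording gives the right answer under either meaning of intake, so it carries no risk. With daily dosing at or below 10 mg, it also keeps compliance from exceeding 100%. The cost is one line of SAP text and the matching line of code. SAP 7.1.2 requires such changes before the database is frozen.
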